## **16 Appendix 4: Guidelines for the management of renal dysfunction**

### **General principles:**

Glomerular filtration rate in HF patients depends on intrinsic renal function and on a balance between afferent and efferent glomerular arterial tonicity. This tonicity is partly regulated by a stimulation of angiotensin II and could be affected by either study medication. Moreover, renal dysfunction may develop or may deteriorate in some patients after study drug administration. These recommendations have been developed to guide the investigators in managing patients with renal dysfunction after randomization.

### **Two types of response to serum creatinine increase are described:**

#### **Surveillance situation**

If, at any time after randomization, eGFR decreases by  $\geq 25\%$  from baseline (or if serum creatinine concentration increase to 2.5 mg/dL [221  $\mu\text{mol/L}$ ]), the investigator will check for potentially reversible causes of renal dysfunction such as:

- Non-steroidal anti-inflammatory drug intake, antibiotics, or other treatments known to affect creatininemia
- Volume decrease, including that resulting from excessive dosing of diuretics
- Urinary infection
- Urinary tract obstruction
- Study medication

#### **Action situation**

If a patient's eGFR decreases by  $\geq 40\%$  from baseline (or if serum creatinine concentration rises above 3 mg/dL (265  $\mu\text{mol/L}$ )), the investigator will check for potentially reversible causes of renal dysfunction (see above).

If the investigator judges that study medication has to be stopped, he/she will have to contact the Novartis medical monitor or his/her designee. Thereafter, serum creatinine assessments will have to be repeated at least each week until levels return to acceptable values. If study medication was stopped, every effort will be done to restart it again, according to clinical conditions.

## 17 Appendix 5: Specific Renal Alert Criteria and Actions

**Table 17-1 Specific Renal Alert Criteria and Actions**

Serum Event	
Serum creatinine increase 25 – 49% compared to baseline	Confirm 25% increase after 24-48h Follow up within 2-5 days
Acute Kidney Injury: Serum creatinine increase $\geq$ 50% compared to baseline	Follow up within 24-48h if possible Consider study treatment interruption Consider patient hospitalization /specialized treatment
Urine Event	
New dipstick proteinuria $\geq$ 1+ Albumin- or Protein-creatinine ratio increase $\geq$ 2-fold Albumin-creatinine ratio (ACR) $\geq$ 30 mg/g or $\geq$ 3 mg/mmol; Protein-creatinine ratio (PCR) $\geq$ 150 mg/g or $>$ 15 mg/mmol	Confirm value after 24-48h Perform urine microscopy Consider study treatment interruption / or discontinuation
New dipstick glycosuria $\geq$ 1+ not due to diabetes	Blood glucose (fasting) Perform serum creatinine, ACR
New dipstick hematuria $\geq$ 1+ not due to trauma	Urine sediment microscopy Perform serum creatinine, ACR
For all renal events:	

Document contributing factors in the CRF: co-medication, other co-morbid conditions, and additional diagnostic procedures performed
 
Monitor patient regularly (frequency at investigator's discretion) until either:
 
Event resolution: sCr within 10% of baseline or protein-creatinine ratio within 50% of baseline, or
 
Event stabilization: sCr level with <math>\pm</math>10% variability over last 6 months or protein-creatinine ratio stabilization at a new level with <math>\pm</math>50% variability over last 6 months.

26-Mar-2019	Prior to DB Lock	Creation of Amendment 1	
 Updated to align with protocol versions 01 and 02 (amended protocols) dated 10-Jun-2018 and 15-Mar-2019, respectively: escalate the echo endpoints from [REDACTED] secondary objectives; add the echocardiographic parameters of Left Ventricular end systolic and diastolic volume indices, LVESVi and LVEDVi, to the secondary endpoints at 12 weeks [REDACTED] Ensured study objectives wording matched that of protocol Specified that geometric means and confidence intervals will be presented for biomarker data Updated baseline definition Removed “on treatment” terminology and “28 days post last dose of study treatment” lag time (from the open-label phase definition) Clarified definitions for double-blind and open-label phases, and changed terminology from “treatment phase” to “study phase” Clarified definitions for date of last administration of study treatment for double-blind phase and for the study 	
 Section 1 Introduction; Section 1.2 Study Objectives and Endpoints; Section 2.3.3 Demographics and Other Baseline Characteristics; Section 2.7.1 Secondary Endpoints; Section 2.7.2 Statistical Hypothesis, Model, and Method of Analysis; [REDACTED] Section 1.2 Study Objectives and Endpoints Section 2.1 Data analysis general information Section 2.1.1 General Definitions Section 2.1.1 General Definitions Section 2.1.1 General Definitions Section 2.1.1 General Definitions Section 2.1.1 General Definitions Section 2.2 Analysis Sets Section 2.3.3 Demographics and Other Baseline Characteristics; Section 2.4.2 Prior, Concomitant and Post Therapies; Section 2.8.1.1 Coding of AEs; Section 5.2 AEs Coding/Grading

Date	Time point	Reason for update	Outcome for update	Section and title impacted (Current)
			8. Clarified definition of date of last contact	11. Section 2.3.3 Demographics and Other Baseline Characteristics
			9. Modified PPS definition to clarify that major protocol deviations will exclude patients from the PPS regardless of the study phase in which they occur	12. Section 2.3.3 Demographics and Other Baseline Characteristics; [REDACTED]
			10. Clarified coding dictionary versions to be utilized	13. Section 2.3.3 Demographics and Other Baseline Characteristics
			11. Clarified that tables summarizing demographics and baseline data will be run only on the FAS	14. Section 2.4.2 Prior, Concomitant and Post Therapies
			12. Indicated that values of the hemodynamic variable carotid-femoral pulse wave velocity will be negative inverse transformed prior to analysis	15. Section 2.5.4 Supportive Analyses 16. Section 2.7.2 Statistical Hypothesis, Model, and Method of Analysis; Section 2.12 Biomarkers;
			13. Removed Chronic Renal Insufficiency from CV history	[REDACTED] 17. Section 2.7.2 Statistical Hypothesis, Model, and Method of Analysis
			14. Added separate summaries of prior and concomitant CV, HF, ACEi and ARB medications	18. Section 2.7.2 Statistical Hypothesis, Model, and Method of Analysis;
			15. Added supportive analyses of the primary endpoint: On-treatment analysis, analysis using the “original” aortic characteristic impedance variable, analysis using the “alternative” aortic characteristic impedance variable	[REDACTED] 19. Section 2.8.1.2 General Rules for AE Reporting; Section 2.8.2 Deaths 20. Section 2.8.1.3 AE Summaries
			16. Removed references to U-creatinine	21. Section 2.8.1.4 Adverse Events of Special Interest/Grouping of AEs; Section 2.8.4.3 Angioedema
			17. Added on-treatment analyses of the secondary endpoints	22. Section 2.8.3 Laboratory data
			18. Clarified correlation analyses of changes from baseline to	

Date	Time point	Reason for update	Outcome for update	Section and title impacted (Current)
			Week 4 trough, and changes from trough to 4 hours post dose at Week 4	23. Section 2.8.3 Laboratory data
			19. Modified definition of treatment emergent AEs and flagging of deaths in listing to remove “28 days post last dose of study treatment” lag time	24. Section 2.8.4.1 Vital Signs
			20. Added AE overview table (number and percentage of patients in various AE categories), two SAE tables (occurring with frequency $\geq 0.5\%$; by seriousness criteria), and most frequent non-SAEs ($\geq 5\%$) table	25. Section 2.12 Biomarkers
			21. Clarified that separate summaries/analyses of angioedema data, including AEs related to angioedema, will be produced – one based on all angioedema and the other based on positively adjudicated angioedema	
			22. Specified conversion factors for lab values indicated as <x or >	27. Section 5.3.2 Notable Laboratory Analyses
			23. Added separate summaries of the incidence of hyperkalemia and worsening renal function through Week 12 based on central laboratory data	28. Section 5.6 Rule of Exclusion Criteria of Analysis Sets
			24. Added summary of the incidence of hypotension through Week 12	

5.1.3	Concomitant medication date imputation	36
5.2	AEs coding/grading	37
5.3	Laboratory parameters derivations	37
5.3.1	Laboratory grading.....	37
5.3.2	Notable laboratory values	37
5.4	Vital signs	38
5.4.1	Notable vital sign values	38
5.5	Statistical models	38
5.5.1	Primary analysis	38
5.5.2	Key secondary analysis	39
5.6	Rule of exclusion criteria of analysis sets.....	39
6	Reference.....	41

List of abbreviations

ACEi	Angiotensin Converting Enzyme Inhibitor
AE	Adverse Event
ANCOVA	Analysis of Covariance
ARB	Angiotensin Receptor Blocker
ATC	Anatomical Therapeutic Chemical
BID	bis in diem/twice a day
BMI	Body Mass Index
BNP	B-type Natriuretic Peptide
CABG	Coronary Artery Bypass Graft
CKD	Chronic Kidney Disease
CRO	Contract Research Organization
CRT-P	Cardiac resynchronization therapy – no ICD
CRT-D	Cardiac resynchronization therapy – with ICD
CSR	Clinical Study report
CTCAE	Common Terminology Criteria for Adverse Events
DCT	Data Collection Tool
eCRF	Electronic Case Report Form
ED	Emergency Department
eGFR	Estimated Glomerular Filtration Rate
FAS	Full Analysis Set
H0	Null Hypothesis
HA	Alternative Hypothesis
HF	Heart Failure
hs-TnT	High Sensitivity Troponin
ICD	Implantable Cardioverter Defibrillator
IRT	Interactive Response Technology
LOCF	Last Observation Carried Forward
LV	Left Ventricular
LVEF	Left Ventricular Ejection Fraction
MRI	Magnetic Resonance Imaging
MedDRA	Medical Dictionary for Regulatory Activities
NT-proBNP	N-terminal Prohormone of B-type Natriuretic Peptide
NYHA	New York Heart Association
PCI	Percutaneous Coronary Intervention
PD	Pharmacodynamic
PK	Pharmacokinetic
PPS	Per-Protocol Set
PRO	Patient-reported Outcomes
PT	Preferred Term
RS	Randomized Set
SAE	Serious Adverse Event

SAP	Statistical Analysis Plan
SOC	System Organ Class
SS	Safety Set
TEAE	Treatment-emergent Adverse Event
TFLs	Tables, Figures, Listings
TIA	Transient Ischemic Attack
█	█
U-cGMP	Urine-cyclic Guanosine Monophosphate
WHO	World Health Organization

1 Introduction

The statistical analysis plan (SAP) will outline in detail the analyses planned in the protocol. The analyses will be used to generate the Clinical Study Report (CSR). The SAP is based on protocol version 02 (amended protocol) dated 15-Mar-2019 and the data collection tool (DCT) version 11.0 dated 23-Jan-2019.

1.1 Study design

This study will use a multicenter, randomized, double-blind, double-dummy, parallel group, active-controlled, forced titration, 12-week design in patients with heart failure and reduced left ventricular ejection fraction (LVEF) $\leq 40\%$. The study duration is a maximum of 30 weeks, including the screening epoch, with 8 scheduled outpatient visits. A total of approximately 432 patients randomized to sacubitril/valsartan or enalapril in a 1:1 ratio is planned with no stratification at approximately 80 centers in the United States.

At the time of randomization, patients will have been on stable treatment with guideline-directed therapy for heart failure with reduced ejection fraction, other than angiotensin converting enzyme inhibitors (ACEi) and angiotensin receptor blockers (ARB), and on an optimal medical regimen to effectively treat co-morbidities such as hypertension, diabetes mellitus and coronary artery disease. All patients will need to meet all other inclusion and none of the exclusion criteria.

Patients will be randomized to either sacubitril/valsartan 24/26 mg bis in diem/twice a day (BID) or enalapril 2.5 mg BID (Dose Level 1), according to the product label(s). Forced titration will occur every 2 weeks to reach the target dose of sacubitril/valsartan 97/103 mg BID or enalapril 10 mg BID (Dose Level 3). Dose level 2 is defined as sacubitril/valsartan 49/51 mg BID or enalapril 5 mg BID. Dose adjustments will only be allowed if indicated per protocol defined safety and tolerability criteria and investigator judgement, or if the investigator believes that adjustment/elimination of concomitant medications is not possible or does not alleviate the side effects of concern. After 12 weeks of double-blind treatment, patients will continue into the 12 week open-label extension.

All patients will need to have a 36-hour washout from study treatment prior to starting the open-label extension to ensure that the blinding of the core study is maintained and to reduce the risk of angioedema. All patients will start open-label treatment on sacubitril/valsartan Dose Level 2, unless they completed double-blind treatment on Dose Level 1. Instead, these patients will enter the open-label extension on sacubitril/valsartan Dose Level 1. Study treatment will be force-titrated every 2 weeks to reach the target dose of sacubitril/valsartan (Dose Level 3).

All eligible patients will be randomized via Interactive Response Technology (IRT) to one of the treatment arms. The investigator or his/her delegate will contact the IRT after confirming that the patient fulfills all the inclusion/exclusion criteria. The IRT will assign a randomization number to the patient, which will be used to link the patient to a treatment arm and will specify a unique medication number for the first package of study drug to be dispensed to the patient.

The randomization numbers will be generated using the following procedure to ensure that treatment assignment is unbiased and concealed from patients and investigator staff. A patient

randomization list will be produced by the IRT provider using a validated system that automates the random assignment of patient numbers to randomization numbers. These randomization numbers are linked to the different treatment arms, which in turn are linked to medication numbers. A separate medication list will be produced by or under the responsibility of Novartis Drug Supply Management using a validated system that automates the random assignment of medication numbers to packs containing the investigational drug(s).

The primary analysis time point will be Week 12.

[figure not shown]
There are no interim analyses planned.

[figure not shown]
1.2 Study objectives and endpoints

The primary objective is to determine whether treatment with sacubitril/valsartan provides a superior effect on aortic characteristic impedance compared to enalapril in patients with heart failure and reduced ejection fraction (LVEF $\leq 40\%$) after 12 weeks of treatment. The primary endpoint is the change in aortic characteristic impedance ($Z_c = dP/dQ$ in early systole) between baseline and Week 12.

The secondary objectives are:

1. To evaluate the effect of sacubitril/valsartan vs. enalapril after 12 weeks of treatment on change from baseline in N-terminal Prohormone of B-type Natriuretic Peptide (NT-proBNP).
2. To evaluate the effect of sacubitril/valsartan vs. enalapril after 12 weeks of treatment on the changes from baseline in echocardiographic measures including:
 - a. Global longitudinal strain
 - b. Left atrial volume index
 - c. Mitral annular E' velocity (Doppler Tissue Imaging)
 - d. Mitral E/E'
 - e. LVEF
 - f. Ventricular-vascular coupling (Ea/Es)
 - g. LV end systolic and diastolic volume indices
3. To evaluate the effect of sacubitril/valsartan vs. enalapril after 4 weeks of treatment on the relation between the change in aortic characteristic impedance and change in biomarker levels, including B-type Natriuretic Peptide (BNP) and Urine-cyclic Guanosine Monophosphate (U-cGMP)/U-creatinine, during both trough and 4 hours post-dose.

2 Statistical methods

2.1 Data analysis general information

 a Novartis-designated Contract Research Organization (CRO) will be performing all analyses outlined in this SAP. SAS[®] version 9.3 (or higher) will be used for all analyses.

Data from all centers that participate in this protocol will be combined, so that an adequate number of patients will be available for analysis.

Unless otherwise specified, for continuous data, the mean, standard deviation, median, first and third quartiles, interquartile range, and minimum and maximum values will be presented. Geometric means and 95% confidence intervals will also be presented for biomarker data. For categorical data, frequencies and percentages will be presented. All statistical tests will be conducted against a two-sided alternative hypothesis, employing a significance level of 0.05.

All data will be provided in listings in addition to summaries described below.

2.1.1 General definitions

Study treatment

Patients will receive either sacubitril/valsartan or enalapril during the first 12 weeks of the study. Study treatment will refer to either of these two drugs.

Baseline

In general, baseline is defined as the last non-missing assessment prior to or on the start date of study treatment (randomization date for patients not treated). For hemodynamic variables baseline is defined as the assessment with a planned time point value of 'Visit_1_Baseline'.

Unscheduled assessments will be excluded from the determination of baseline.

Date of first administration of study treatment

Double-blind phase: The date of first administration of study treatment in the double-blind phase is defined as the first date a dose of study treatment is administered and recorded on the Dosage Administration Record - At Visit (Visit 2) electronic case report form (eCRF).

Open-label phase: The date of first administration of study treatment in the open-label phase is defined as the first date a dose of sacubitril/valsartan is administered in the open-label phase and recorded on the Dosage Administration Record - At Visit (Visit 7) eCRF.

Date of last administration of study treatment

Double-blind phase: The date of last administration of study treatment in the double-blind phase is defined as the last date a dose of study treatment is administered in the double-blind phase and recorded on the Dosage Administration Record - At Visit (Visit 6) eCRF. In the event this date is not available from the Dosage Administration Record - At Visit (Visit 6) eCRF, it will

be determined from the End of Study Treatment eCRF or Dosage Administration Record - Summary eCRF.

Open-label phase: The date of last administration of study treatment in the open-label phase is defined as the last date a dose of sacubitril/valsartan is administered in the open-label phase and recorded on the Dosage Administration Record - Summary eCRF.

The date of last administration of study treatment during the study is defined as the last date a dose of study treatment is administered and recorded on the End of Study Treatment eCRF. In the event this date is not available from the End of Study Treatment eCRF, it will be obtained from the Dosage Administration Record - Summary eCRF.

Study day

The study day describes the day of the assessment relative to the date of randomization.

The study day will be calculated as the difference between the date of assessment and the date of randomization plus 1. If the date of assessment is prior to the date of randomization, the study day will be negative and will be calculated as the difference between the date of the assessment and the date of randomization.

Double-blind phase

Assessments performed at Weeks 1, 2, 4, or 12 (including, but not limited to, vital signs) will be assigned to the double-blind phase for summarization purposes. Unscheduled assessments are not assigned to a study phase for purposes of by-visit summaries.

For summarization of adverse events [AEs], medications, protocol deviations, notable vital signs and laboratory abnormalities, angioedema, and hospitalizations/ED visits/unplanned outpatient clinic visits due to worsening HF symptoms by study phase, an assessment during the double-blind phase is defined as any assessment obtained in the following time interval:

Date of randomization (or date of first administration of study treatment, as appropriate) through the date of the Week 12 visit, inclusive. For patients without a Week 12 visit, a projected Week 12 visit date will be derived relative to their randomization date.

Open-label phase

Assessments performed at Weeks 14 or 24 (including, but not limited to, vital signs) are assigned to the open-label phase for summarization purposes. Unscheduled assessments are not assigned to a study phase for purposes of by-visit summaries.

For summarization of AEs, medications, protocol deviations, notable vital signs and laboratory abnormalities, angioedema, and hospitalizations/ED visits/unplanned outpatient clinic visits due to worsening HF symptoms by study phase, an assessment during the open-label phase is defined as any assessment obtained in the following time interval:

After the date of the Week 12 visit. For patients without a Week 12 visit, a projected Week 12 visit date will be derived relative to their randomization date.

Patients who died, withdrew consent, or were lost to follow-up prior to or on their projected Week 12 visit date will be excluded from the open-label phase.

Last contact

The date of last contact will be determined as the later of the following dates:

- The last visit date for each patient derived by examining all visit data collected in the eCRFs
- Date of discontinuation/study phase completion for the double-blind and open-label phases

Year, month and week

For reporting purposes, the rules below will be followed to convert a year, month and week to days.

1 year = 365.25 days

1 month = 30.3475 days

1 week = 7 days

1 day = 24 hours

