### Open-label extension epoch

The purpose of this open-label period is to observe the additional vascular effects of sacubitril/valsartan that occur beyond 12 weeks of treatment.

After 12 weeks of successful double-blind, active treatment, patients will continue into the 12 week open-label extension epoch. Patients will have received the final dose of double-blind treatment medication in the clinic at Week 12 (Visit 6).

- ALL patients will need to have a 36-hour washout from study treatment prior to starting the open-label extension to ensure that the blinding of the core study is maintained and to reduce the risk of angioedema.
- To facilitate this washout, patients will be instructed NOT to start their open-label treatment until the evening of the following day.
- All patients will start open-label treatment on sacubitril/valsartan 49/51 mg BID (Dose level 2), unless they completed the double-blind treatment epoch on Dose Level 1. Instead, these patients will enter the open-label epoch on sacubitril/valsartan 24/26 mg BID dose (Dose level 1).
- Study treatment will be force-titrated every 2 weeks to reach the target dose of sacubitril/valsartan 97/103 mg BID (Dose Level 3).

Deviation from the titration schedule or dose adjustments will only be allowed if indicated per protocol defined safety and tolerability criteria (See [Section 5.5.5](#), [Table 5-7](#)), and investigator judgement, if the investigator believes that adjustment/elimination of concomitant medications is not possible or does not alleviate the side effects of concern.

Follow-up safety visits will occur throughout the study at Weeks 1, 2, 4, 12, 14 and 24 (Visits 3, 4, 5, 6, 7, and 8).

Primary efficacy assessments will be conducted at Screening/Baseline, Day 1 (Visit 2) pre-randomization, and Week 12 (Visit 6).

[figure not shown]
Patients will be contacted by phone at approximately 30 days following the last administration of study treatment at Week 24 (Visit 8), or early withdrawal, in order to determine if any SAE(s) occurred during this time period. These SAEs will be recorded in the source document only and must be reported to Novartis. Attempts to contact the patient should also be recorded in the source document.

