- At Week 12 (Visit 6), patients will have the final dose of double-blind treatment medication administered in the clinic after pre-dose assessments have been completed. Drug accountability will be performed and all double-blind treatment medication will be returned to the site.
- All patients that complete the 12 week (Visit 6) double-blind treatment epoch will proceed into the 12-week open-label epoch on sacubitril/valsartan.
- Open-label sacubitril/valsartan will be dispensed at Week 12 (Visit 6) with patient instructions **NOT** to start their open label-treatment until the evening after completing a 36-hour wash out. All patients will have the wash out in order to maintain the blinding of the core study.

All dose levels will be available throughout the study. Dose adjustments to lower dose levels may be made at any time at both scheduled and unscheduled visits only if indicated for blood pressure control/tolerability reasons.

All study treatment assigned by the IRT will be recorded/databased in the IRT.

All dosages prescribed and dispensed to the patient and all dose changes during the study must be recorded in the IRT and on the Dosage Administration Record eCRF.

Study medication should be taken twice daily with a glass of water with or without food. Prior to scheduled study visit days, instruct the patient to have nothing by mouth after midnight and to take study medication after vital signs and study assessments are taken by the study coordinator at the investigator site.

If the patient misses taking any study drug dose, he/she should take it as soon as possible and within 4 hours of the scheduled dose time. If the patient is unable to take the missed dose within 4 hours of the scheduled dose time, he/she should skip the missed dose and return to his/her regular study drug administration schedule.

The investigator must promote compliance by instructing the patient to take the study treatment exactly as prescribed and by stating that compliance is necessary for the patient's safety and the validity of the study. The patient must also be instructed to contact the investigator if he/she is unable for any reason to take the study treatment as prescribed.

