## **6 Visit schedule and assessments**

[Table 6-1](#) lists all of the assessments and indicates with an "X" when the visits are performed. Assessments that will only be reported in the source documentation are marked with an 'S'.

Patients must be seen for all visits on the designated day, or as close to it as possible, including those on dose interruptions or discontinued treatment. A visit window of +/- 3 days is allowed. Every effort should be made to respect the time frame for the primary efficacy endpoint at Week 12 (Visit 6) visit.

Missed or rescheduled visits should not lead to automatic discontinuation. Patients who prematurely discontinue the study for any reason should be scheduled for a visit as soon as possible, at which time all of the assessments listed for Visit 6 (End of Treatment) or Visit 8 (End of Study) will be performed, depending on the epoch from which the patient prematurely discontinues from the study. See [Section 5.6.3](#). At this final visit, all dispensed investigational product should be reconciled and the adverse event and concomitant medications reconciled on the eCRF.

[figure not shown]
Patients will be contacted by phone at approximately 30 days following the last administration of study treatment, Week 24 (Visit 8), or early study discontinuation, in order to determine if any SAE(s) occurred during this time period. These SAE(s) will be recorded in the source document only and must be reported to Novartis. Attempts to contact the patient should be recorded within the source document.

Every SAE occurring after the patient has provided informed consent and until 30 days following the last administration of study treatment must be reported directly to the Novartis Drug Safety and Epidemiology Department within 24 hours of learning of its occurrence.

Unscheduled visits for safety/medication evaluation/unscheduled assessments are permitted at any time during the study.

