## 6.3 Treatment exposure and compliance

Compliance will be assessed by the investigator, and/or study personnel, at each visit using pill counts and information provided by the patient. This information should be captured in the source document at each visit. All study treatment dispensed and returned must be recorded in the Drug Accountability Record.

Patient compliance should be at least 80% during the double-blind treatment period. The investigator and/or study personnel will counsel the patient if compliance is below 80%. Study drug accountability will also be determined by the site monitor while performing routine site visits and at the completion of the study.

Duration of double-blind study drug exposure will be calculated based upon the start and end dates recorded in the Dosage Administration Record eCRF.

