## **9.3 Treatments**

The overall duration on the double-blind study drug will be summarized by treatment group using mean, standard deviation, median, 25th and 75th percentiles, interquartile range, minimum, and maximum. Additionally, the number and percentage of patients will be summarized by treatment group for duration category.

Concomitant medications and significant non-drug therapies, prior to and after the randomization date will be summarized (frequency and percent) by therapeutic class, preferred term, and treatment group.

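### The SAP takes the first open-label dose date only from the Visit 7 form (planned Day 98), although open-label drug starts on planned Day 85, and it names no fallback form

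*SAP*

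**What the plan says.** **Source of the date.** SAP 2.1.1 gives the first open-label date as the earliest day on which "a dose of sacubitril/valsartan is administered in the open-label phase and recorded on the Dosage Administration Record - At Visit (Visit 7) eCRF". It names no other form.

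**Use of the date.** SAP 2.4.1 computes open-label duration as last minus first open-label date plus 1. It also plans weekly duration categories and total patient-days by study phase.

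**When drug starts.** The final double-blind dose is given in the clinic at Visit 6, and open-label drug is dispensed at that visit (Protocol 5.5.4). On the start, Protocol 3.1 says: "To facilitate this washout, patients will be instructed NOT to start their open-label treatment until the evening of the following day".

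**Other dates in the same section.** If the last double-blind date is not on the Visit 6 form, SAP 2.1.1 says that it will "be determined from the End of Study Treatment eCRF or Dosage Administration Record - Summary eCRF". The last dose in the study also has a fallback. SAP 5.1.1 rules out imputing study treatment dates.

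**What the dosing record holds.** Protocol 6.3 says: "Duration of double-blind study drug exposure will be calculated based upon the start and end dates recorded in the Dosage Administration Record eCRF". Protocol 5.5.4 adds that prescribed and dispensed dosages and "all dose changes during the study must be recorded in the IRT and on the Dosage Administration Record eCRF". Neither says what the Visit 7 page contains.

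**The concern.** The only named source belongs to a visit about two weeks after the drug is started. If the Visit 7 page records that day's clinic dose, the first open-label dose step disappears from every patient's exposure. Patients who stop during that step get no duration at all. They are the shortest-exposed patients, so their loss from the summary would not be random.

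If the page does record the earlier home start, the date is right wherever the page exists. A patient who started the drug but has no Visit 7 page then still has no start date, and imputation is ruled out.

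At stake is the accuracy of the open-label exposure tables, not any treatment comparison.

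**Working it through.** **Inputs**
- Visits 6, 7 and 8: planned Days 84, 98 and 168 (Protocol Table 6-1).
- First open-label dose: the evening after Visit 6, Day 85 (Protocol 3.1). As a check, suppose the Visit 6 dose is taken within the 07:00 to 11:00 trough window of Protocol 6.4.1 (our assumption). Adding the 36-hour washout gives 19:00 to 23:00 the next day, which agrees.
- Last open-label dose: Day 168, because Week 24 has a post-dose assessment (Protocol 6.4.1).
- Visit window: "A visit window of +/- 3 days is allowed" (Protocol 6).
- Planned open-label length: 12 weeks (Protocol 5.1.1). Planned open-label patients: about 346 (Protocol Table 5-3).
- Formula: duration = last date − first date + 1 (SAP 2.4.1).

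**1. Reproduce the plan's length.** 168 − 85 + 1 = 84 days, and 12 × 7 = 84. A Day 85 start gives exactly the planned 12 weeks.

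**2. If the Visit 7 form holds the clinic dose.** 168 − 98 + 1 = 71 days. The shortfall is 84 − 71 = 13 days, and 13/84 = 15.5%.

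**3. Visit windows, same reading.** Shortfall = Visit 7 day − (Visit 6 day + 1).
- Smallest: 95 − (87 + 1) = 7 days.
- Largest: 101 − (81 + 1) = 19 days.

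**4. Weekly categories, same reading.** At planned days a completer moves from 84 to <91 days down to 70 to <77 days, which is two categories. Over all 343 combinations of window days for Visits 6, 7 and 8, the move is one category in 84, two in 224 and three in 35.

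**5. Early stoppers at planned days, same reading.**
- Last dose on Days 85 to 97: true duration 1 to 13 days, but no Visit 7 clinic dose, so no start date.
- Last dose on Day 98: true 98 − 85 + 1 = 14 days; by the SAP rule 98 − 98 + 1 = 1 day.
- Last dose on Day 110: true 110 − 85 + 1 = 26 days; by the SAP rule 110 − 98 + 1 = 13 days.

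The two lowest categories (under 14 days) would therefore hold patients truly treated for 14 to 26 days. Those truly treated for under 14 days would be missing.

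**6. Patient-days, if all 346 complete on schedule.** 346 × 84 = 29,064 and 346 × 71 = 24,566. The difference is 4,498 on the clinic-dose reading.

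**7. If the form has a home-start field.** The first date is Day 85, the duration is 84 days and the shortfall is 0. A patient with no Visit 7 form still has no first date.

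**8. Fallbacks across SAP 2.1.1.** The section defines five first- or last-dose dates.
- Two have a fallback: last double-blind and last in the study.
- Three have a single source: first double-blind, first open-label and last open-label.

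Of the five, only the first open-label date is tied to the form of a visit that comes after the dose it should date.

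**The case against.** The strongest reply is that the 13 days rest on a form that the documents do not show. The SAP's words can be read as meaning the first open-label dose wherever it was taken. Visit 7 is the first visit after the home start, so its page is a natural place to record that start. The authors wrote from a stated version of the data collection tool and had the form in front of them. Note 16 to Table 6-1 tells patients to take the visit-day morning dose in the clinic; it does not describe form fields. All of this stands. A reader might infer that completers' exposure will certainly be understated, and the documents do not support that.

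The lack of a fallback is also not peculiar to this date, since two others in the section have a single source. That stands as well. However, the first double-blind date comes from the form of the visit where that dose is given, and the last open-label date comes from a summary form. Neither has this mismatch in timing.

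Patients who stop drug are still expected at scheduled visits (Protocol 5.6.2 and 6). With a home-start field, the gap is therefore confined to patients who started the drug and have no Visit 7 form. Their number cannot be estimated from the documents.

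Finally, the output is descriptive and covers one drug. Of double-blind drug, Protocol 9.3 says: "The overall duration on the double-blind study drug will be summarized by treatment group"; it asks for no open-label duration. SAP 2.4.1 also lists all dose administration data, so recorded dates stay visible. These points limit the importance but do not supply the missing source.

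**Conclusion.** The point holds as a minor correction. The SAP ties the first open-label dose to a form from a visit 13 days later at planned visit days, does not say which field is meant, and gives no alternative source.

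The size depends on the form:
- **Clinic dose:** 13 days short per planned completer, with no start date for patients who stop before Visit 7. The use of the Visit 2 and Visit 6 forms for doses at those visits points this way but does not prove it.
- **Home-start field:** no shortfall for patients with the form, and no computable duration for those without it.

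The patient-day figure also assumes that every planned open-label patient completes on schedule.

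A reader might infer that adverse event percentages or the primary result are affected. They are not affected by this date: SAP 2.1.1 splits adverse events by phase at the Week 12 visit date (actual or projected), and the primary comparison is made at Week 12.

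**What to change.** Check the eCRF, then reword the definition in SAP 2.1.1:
- Take the first open-label dose date from the form or field that records the first home dose. One candidate is the Dosage Administration Record - Summary form, already the source of the last open-label dose, if it holds that date. If the Visit 7 form has a home-start field, name that field.
- Name a second recorded form to use when the main one is missing, as is done for the last double-blind dose. Taking a recorded date from another form is not imputation, so SAP 5.1.1 needs no exception.

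The cost is a few words of SAP text and one derivation, provided that a suitable date is already collected. Protocol 6.3 mentions start and end dates only for double-blind drug, so the eCRF check has to come first.
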